4. OBJECTIVES*

We propose to prospectively randomize orthopedists, with their patients, to receive (or not) a real-time, web-based system intervention: the OA Care plan. The OA Care plan will include individualized, patient-centric information: (1) trended patient-reported OA pain and function, (2) tailored estimates of likely TJR benefits and risks based on a contemporary US cohort of 25,000 TJR patients (FORCE-TJR Registry), (3) evidence-based information for non-operative care, and (4) individual patient goals.

Specific Aims include:

Aim 1. Patients and their Caregivers/Trusted Others will refine the design, content, and usability of a real-time, web-based individual OA Care plan to guide TJR and non-operative OA care decisions.

Aim 2. Randomize 40 orthopedists, and their patients, to receive the OA Care plan at the time of orthopedic consultation (intervention) vs. usual care (control) and compare (a) OA care decision process and quality and (b) quality of OA care as measured by pain relief and functional gain in the two arms at 6 and 12 months after the decision, and assess the impact of decision quality on quality of OA care.

Aim 3. Randomize 36-40 orthopedists, and their patients, to receive the OA Care plan plus peer, family, and primary care physician support (OA Care plan+Support; intervention called A.S.K. Coaching) vs. the OA Care plan alone and compare the quality of OA care decision and quality of care (pain relief, functional gain) in the two arms.

When moving the PCORI contract to Northwestern in early 2019, we revised the sample size estimates required to meet the same study power and analytic plan for both Aim 2 and Aim 3. Using the early study data, we determined that n=3000 patients in Aim 2 and n=3000 patients in Aim 3 was adequate to meet statistical goals. We also determined that fewer surgeons (N= 36-40) would be required in Aim 3 to consent 3000 patients. PCORI agreed to the changes in number of surgeons and patients. We clarified this change in the ISP.

Based on the components of the Chronic Care Model, this technology-delivered, individualized OA Care plan will enable patients and clinicians to make treatment decisions based on patient symptoms, goals, and comparative effectiveness evidence. We hypothesize that OA Care plan users, as compared to usual care, will report greater decision quality for both TJR or non-

INVESTIGATOR STUDY PLAN

12.14.2021

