7. STUDY-WIDE NUMBER OF SUBJECTS*

Aim 1 Patient Interviews= 30 participants

Caregiver/Trusted Other Interviews = 30 participants

Aims 2 and 3 6000 patients total, 3000 in Aim 2 and 3000 in Aim 3

20-30 surgeon offices will have 1-2 surgeons for each office (total 40 surgeons) contribute 100 consecutive new patients to the study for Aim 2 and an additional 100 patients for Aim 3.

For surgeon qualitative interviews: up to 35 MD surgeons. MD surgeons are not subjects in the ASK study (patients are).

For Aim 3 patient qualitative interviews: Up to 50 patients, with an approximately even breakdown from each of the following groups

- Participated in A.S.K. Coaching + self-reported (on 1-month survey) surgery planned and use of OA Care plan with MD.
- Participated in A.S.K. Coaching + self-reported (on 1-month survey) non-surgical treatment planned and use of OA Care plan with MD.
- Participated in A.S.K. Coaching + self-reported (on 1-month survey) surgery planned and no use of OA Care plan with MD.
- Participated in A.S.K. Coaching + self-reported (on 1-month survey) non-surgical treatment planned and no use of OA Care plan with MD.
- Usual Care arm + self-reported (on 1-month survey) surgery planned and use of OA Care plan with MD.
- Usual Care arm + self-reported (on 1-month survey) non-surgical treatment planned and use of OA Care plan with MD.

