12. DATA AND SPECIMEN BANKING*

No specimens will be banked for future use. See #13, Data Management, for data retention and access.

13. Data Analysis and Management*

Responsibility for 6 month and 12 month outcome data collection was transferred from UMMS to Northwestern during 2021. At the completion of study enrollment (on or about March 1, 2022), the UMMS data enrollment and collection services will be completed. At that date, the UMMS data center will have already, or will then, transfer all enrollment, patient-reported, and study data to Northwestern for the analytic team to manage and analyze. The UMMS data center will confirm that they expunged all ASK study data from the web-based data capture systems (DatStat, RedCap) and UMMS data storage files within UMMS.

Aim 1

We will transcribe recorded interviews and code using content analysis techniques to identify themes. We expect to achieve data saturation at or before completing 30 interviews with patients and 30 with caregivers.

AIM 2 and 3. Sample size and effect size estimates:

The trial is designed with $\geq 80\%$ statistical power at 5% significance level to detect intervention effects that are meaningful to both patients and surgeons, and health systems. In total, 40 (Aim 2) or 54 (Aim 3) surgeons will be randomized equally to treatment and control arms with an average of 100 patients/surgeon. Based on data from FORCE-TJR, the intraclass correlation within surgeon is approximately 0.02. Using two independent group t-tests adjusting for within surgeon clustering, the trial can detect an intervention effect of (a) improved decision quality of >0.16 SD ; (b) improved quality of OA care defined in two ways: 6 month post-decision pain relief (KOOS/HOOS) of ≥ 3.3 points for TKR patients (34.1 vs. 37.4; SD=20.8) and ≥ 3.3 for THR patients (45.7 vs. 49.0; SD=20.9) or greater proportion of patients with meaningful pain relief (17 points in HOOS/KOOS pain score) of $\geq 6.1\%$ more TKR patients (77.9% vs. 84.0%) and $\geq 4.2\%$ more THR patients (90% vs. 94.2%).

Aims 2 and 3: Overview of analytic approach. We hypothesize (Aim 2) that patient/clinician use of the OA Careplan will improve decision quality as well as

INVESTIGATOR STUDY PLAN

12.14.2021

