will be entered into the same model in order to assess their contributions to the outcome under analysis, after adjusting for each other, as well as the patient-level covariates. Model assumptions will be carefully examined. In these model-building processes, effect modifications will be examined by including interaction terms between relevant covariates, and to ensure the heterogeneity of the intervention effects among patient subgroups are adequately considered. The analyses will be conducted with all patients; and then for TKR and THR patients separately. While the primary goal is to understand patient-level covariates with outcomes, it is critical to assess surgeon/site factors that may influence outcome for all, or sub-groups of patients. For example, obese, diabetic patients with cardiac disease may have more positive decision quality and pain relief with a more experienced high-volume surgeon.

Aim 2: To assess the effect of OA Careplan on (a) decision quality and (b) pre-to- post decision pain relief and functional gain, we will do the following. We expect 20 surgeons and 2000 patients will receive the OA Careplan intervention, and another 20 surgeons and 2000 patients will receive usual care. The analyses will be conducted with all patients; and then for TKR and THR patients separately. First, we will tabulate the decision quality and care outcomes by arm and for select patient subgroups (e.g., sex, age, race/ethnicity). Second, we will use GLLAMM to estimate adjusted Careplan intervention effects by including in the models a Careplan indicator (Careplan intervention=1 vs. usual care=0) and a set of site/surgeon and patient variables for adjustment. A statistically significant coefficient of the Careplan indicator signals possible intervention effect. In this analysis, interaction terms between the Careplan indicator and surgeon or patient factors will be examined, statistically significant interaction terms may suggest the existence of heterogeneity in intervention effects. If present, intervention effects will be analyzed and presented by subgroups.

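### Aim 2 cannot have 80% power for 3.3 points in both TKR and THR patients, and the power statement predates the cut to 3,000 patients per aim

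*Combined protocol and SAP*

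**What the plan says.** Section 13 (Sample size and effect size estimates) states at least 80% power at the 5% level. Its basis is a two-group t-test corrected for clustering by surgeon, with an ICC of about 0.02 and 100 patients per surgeon on average: "40 (Aim 2) or 54 (Aim 3) surgeons will be randomized equally to treatment and control arms". The 6-month pain targets are given by joint only: "3.3 points for TKR patients (34.1 vs. 37.4; SD=20.8") and "3.3 for THR patients (45.7 vs. 49.0; SD=20.9"). Responder targets are also by joint: 77.9% vs 84.0% (TKR) and 90% vs 94.2% (THR).

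The Aim 2 paragraph of Section 13 says: "We expect 20 surgeons and 2000 patients will receive the OA Careplan intervention", with the same number in usual care. On analysis it says: "The analyses will be conducted with all patients; and then for TKR and THR patients separately". The Aim 3 paragraph also has 2,000 patients per arm.

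Section 4 reports a 2019 revision, based on early study data and said to preserve power, which found that "n=3000 patients in Aim 2 and n=3000 patients in Aim 3 was adequate to meet statistical goals" and that "fewer surgeons (N= 36-40) would be required in Aim 3 to consent 3000 patients". Section 7 gives the same 3,000 per aim, but also has 20–30 offices with 40 surgeons in total "contribute 100 consecutive new patients to the study for Aim 2 and an additional 100 patients for Aim 3".

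**The concern.** The TKR and THR targets are nearly the same standardised effect as the all-patient decision-quality target (3.3/20.8 = 0.159 and 3.3/20.9 = 0.158, against 0.16 SD). A joint-specific comparison uses only part of the sample, so its detectable difference should be larger than the all-patient one. That it is not suggests the whole arm was counted once for knees and again for hips.

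The paragraph also rests on a design that Sections 4 and 7 have replaced. A reader who meets a null knee-only or hip-only pain result would take it as a null with at least 80% power for 3.3 points, which the plan's own inputs do not support.

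A secondary point is that "TKR patients" and "THR patients" are not defined. Section 10 speaks of hip patients and knee patients, which suggests the index joint. If operated patients are meant, the groups are formed after randomisation by the very decision the Careplan is meant to influence.

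**Working it through.** **Inputs.** From Section 13: k = 20 surgeons per arm in Aim 2 (27 in the superseded Aim 3 design), m = 100 patients per surgeon, ICC = 0.02, difference 3.3, SD 20.8 or 20.9, 5% level. Two-sided testing is assumed because the plan does not say. From Section 4: 3,000 patients per aim, so m = 75 with 40 surgeons or 83.3 with 36. The documents give no knee/hip split, so the splits below are assumptions.

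**Formulas.** Design effect DE = 1 + (m − 1) × ICC. Effective n per arm = k × m / DE. SE = SD × √(2 / effective n). Power = Φ(3.3/SE − 1.96), or noncentral t with 2k − 2 df. Ranges run from t to z and cover both SDs.

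**Reproducing the plan's figure.** With the whole arm in one joint, DE = 1 + 99 × 0.02 = 2.98 and effective n = 2,000/2.98 = 671. For TKR, SE = 20.8 × √(2/671) = 1.136, 3.3/1.136 = 2.906, and Φ(0.946) = 0.828. The t version gives 0.808. THR gives 0.805–0.824. The detectable difference is 3.18–3.28 points, or 0.153–0.157 SD. The responder contrasts also fit this effective n (79–82%). A one-sided 5% test would give 0.136–0.139 SD and 2.8–2.9 points, which does not match the plan.

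**Sharing the arm between joints.** At 50/50, m = 50, DE = 1.98 and effective n = 1,000/1.98 = 505. For TKR, SE = 1.309 and Φ(2.521 − 1.96) = 0.713.

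| Design (surgeons per arm × patients per surgeon in the comparison) | Effective n per arm | Power for 3.3 | Detectable difference |
|---|---|---|---|
| Aim 2 as written, whole sample, 20 × 100 | 671 | 81–83% | 3.2–3.3 |
| Aim 2 as written, 60% share, 20 × 60 | 550 | 72–75% | 3.5–3.6 |
| Aim 2 as written, 50% share, 20 × 50 | 505 | 69–71% | 3.7–3.8 |
| Aim 2 as written, 40% share, 20 × 40 | 449 | 64–66% | 3.9–4.0 |
| Superseded Aim 3, 50% share, 27 × 50 | 682 | 82–83% | 3.2 |
| 3,000 patients, 40 surgeons, whole sample, 20 × 75 | 605 | 76–79% | 3.4–3.5 |
| 3,000 patients, 36 surgeons, whole sample, 18 × 83.3 | 567 | 73–76% | 3.5–3.6 |
| 3,000 patients, 40 surgeons, 50% share, 20 × 37.5 | 433 | 62–65% | 4.0–4.1 |
| 3,000 patients, 36 surgeons, 50% share, 18 × 41.7 | 414 | 60–63% | 4.1–4.2 |

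**Is there a split that works?** For TKR, 80% power needs effective n = 2 × (1.96 + 0.842)² × (20.8/3.3)² ≈ 624 per arm. Solving 20m/(1 + 0.02(m − 1)) = 624 gives m ≈ 81. Across both SDs the requirement is 81–83 per surgeon (z) or 94–96 (t). Two joints cannot each hold 81 of the same 100 patients. At 3,000 patients and 40 surgeons only 75 per surgeon are enrolled in all. With 36 surgeons the need is 111–114 (z) or 135–140 (t), against 83.

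**Other endpoints at 3,000.** At 50/50 the detectable responder differences become 7.3–7.7 percentage points (TKR) and 5.0–5.2 (THR), against the stated 6.1 and 4.2. Decision quality, on all patients, moves only to 0.16–0.17 SD.

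**What would restore 80% at 3,000.** Per joint at 50/50: an ICC of about 0.003–0.006, or covariates explaining 31–38% of the variance. For the whole sample: an ICC of 0.015–0.019, or 3–15% of the variance.

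**Illustration only.** If 70–100% respond at 6 months and 50–100% of each joint group is operated on (both assumed), operated-only power at 50/50 is 35–65%.

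**The case against.** 1. *The figures may be one whole-trial effect expressed on each joint's scale.* The responder contrasts also have effect sizes of h = 0.156 and 0.157, so this is probably how the numbers were made. But the text attaches them to TKR and THR patients, gives no all-patient pain figure, and Section 13 plans separate joint analyses. On this reading the plan has no per-joint power statement at all, and the wording still needs correcting.

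2. *The planned models are stronger than a t-test.* Section 13 adjusts for baseline pain and function, and later pools both phases, with surgeons crossing between conditions. At 3,000 per aim and 50/50, that pooled model gives about 92% per joint for Careplan against usual care with no phase term, but about 65% with one. Without the term, the gain comes from attributing all change between phases to the intervention. Covariates could help, but no explained variance is stated. The plan's declared basis is the unadjusted clustered t-test.

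3. *Section 4 says power was re-estimated.* This stands: the fault is that no revised ICC, SD or detectable difference is shown, not that none was derived. An ICC of 0.01 would give 81–83% per joint at 4,000 and 50/50, but only 72–75% at 3,000 with 40 surgeons.

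4. *Section 7 may mean 100 per office.* Thirty offices would then give exactly 3,000. This is possible, so that sentence is ambiguous rather than plainly wrong.

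5. *Enrolment is nearly over and the joint results are subgroups.* Restated power cannot change the design, and confidence intervals will show the precision. That limits the seriousness but does not make the stated figure correct.

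**Conclusion.** The point holds. On the plan's own Aim 2 inputs, at least 80% power for 3.3 points cannot be true for both joints at any split; an even split gives 69–71% each. This rests on ICC 0.02, the stated SDs, a two-sided test and the t-test basis that Section 13 declares. It is confined to Aim 2, because the 54-surgeon Aim 3 design would have supported both joints at an even split; that design has been replaced.

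Section 13 was also not updated for 3,000 patients per aim. If the old ICC and SDs carry over, the all-patient pain comparison has 73–79% power and each joint 60–65% at an even split, before any non-response. The cut alone costs little, and the double use of the sample is the larger problem. The primary decision-quality comparison is barely affected. The conclusion does not depend on the operated-only question, which is a matter of definition to settle. It should be fixed, but it does not threaten the trial's main comparison.

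**What to change.** - In Section 13, restate the all-patient and per-joint detectable differences for 3,000 patients per aim, with 40 surgeons in Aim 2 and 36–40 in Aim 3. Use the observed joint counts, ICC, SD and 6-month response, and state whether the test is two-sided.
- Show the recalculation that Section 4 refers to. If covariate adjustment or pooling across phases is credited, state the variance explained and whether a phase term is included.
- Withdraw the per-joint 80% claim if it is not met.
- Remove the 54-surgeon, 100-per-surgeon and 2,000-per-arm figures from Section 13, and make Section 7 say whether its 100 is per surgeon or per office.
- Define the joint-specific comparison by index joint at baseline (knee/KOOS or hip/HOOS), operated or not, and label any operated-only comparison as non-randomised.

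The cost is one recalculation with data already in hand and some rewording, with no extra patients or visits. The price is a weaker or withdrawn per-joint power statement.

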If the Research Coordinator is unable to reach the potential participant by phone, the Final contact Recruitment and Follow-up-e-mail-snail mail 2-14-18 letter will be sent to the patient either by email or snail mail (see attached). This letter will also be used if consented participants do not return follow-up surveys.

Surgeon offices will be randomized to Usual Care or Intervention sites. During Aim 2, after completing the surveys in the clinic, usual care patients and surgeons will have the ability to see PRO scores, but will NOT receive feedback (no OA Care Plan). This is the current standard of care in orthopedic clinics. For intervention sites, the patient and surgeon will receive the OA Care Plan (named the A.S.K. Report).

INVESTIGATOR STUDY PLAN

12.14.2021

The DCC will follow-up with patients at 3 time points: 1-month Decisional Conflict Scale and Shared Decision Making Process Survey; 6 months and 12 months after surgery or decision to use non-surgical method of managing OA. (see 1-month Decisional Conflict Scale, 6 and 12-month [Knee/Hip] surveys attached). Surveys will be mailed and/or emailed based on participant preference. The 12 month surveys are standard clinical care; the 1 month, and 6 month contact are for the research. After receiving IRB approval (hopefully September 2020), newly enrolled patients will also respond to Covid-19 measures via the same web-based data capture system used in the rest of the study at 1-month, 6 months and 12 months.

Participants will receive a \$20 gift card after completing the 1-month Decisional Conflict Scale for their time

During Aim 3, Usual Care sites will receive the OA Care Plan (A.S.K. Report), and Intervention sites will receive the Enhanced OA Care Plan, including access to Patient Peer Support website and PCP reports. All surgeons that used the OA Care plan in Aim 2 will be invited to participate in the Enhanced OA Care plan in Aim 3.

When patients are contacted to complete the post-visit 1-month Decisional Conflict Scale, we will inquire as to whether the surgeon and patient reviewed the A.S.K. Report together. This allows us to understand report use rates for all patients.

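### The stated power for pain relief and responders is for operated knee or hip patients, each counted as the whole enrolment; no pain or responder figure covers the all-patient analysis that comes first

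*Combined protocol and SAP*

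**What the plan says.** Section 13 (sample size and effect size estimates) sets at least 80% "statistical power at 5% significance level". It plans for "40 (Aim 2) or 54 (Aim 3) surgeons will be randomized equally to treatment and control arms with an average of 100 patients/surgeon", and derives detectable effects "Using two independent group t-tests adjusting for within surgeon clustering". The stated effects are:

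- decision quality: more than 0.16 SD;
- pain relief, knee: 3.3 "points for TKR patients (34.1 vs. 37.4; SD=20.8");
- pain relief, hip: 3.3 points (45.7 vs 49.0, SD 20.9);
- meaningful pain relief: 77.9% vs 84.0% (knee) and 90% vs 94.2% (hip).

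On clustering it says: "Based on data from FORCE-TJR, the intraclass correlation within surgeon is approximately 0.02". Section 4 describes that source as a "contemporary US cohort of 25,000 TJR patients (FORCE-TJR Registry").

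The enrolled population is wider. Section 6 admits patients at a new evaluation, subject to exclusions, without requiring surgery. Section 8 schedules follow-up "6 months and 12 months after surgery or decision to use non-surgical method of managing OA". The section 13 overview extends the hypothesis to non-operative care, and its Aim 2 text analyses all patients before taking knee and hip replacement separately. Section 10 makes pain relief part of the primary outcome. Sections 4 and 7 now set 3,000 patients per aim.

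**The concern.** The pain and responder inputs belong to people who had a joint replaced, while the first-listed analysis also includes people who did not. A mixed population has a different mean, SD, responder rate and ICC. In particular, if surgeons differ in how often they operate, and operated patients gain more relief, surgeon means differ for that reason too. An ICC estimated among operated patients only cannot contain that component.

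At stake is how a null result on pain would be read. The 3.3-point, 6.1% and 4.2% figures are the plan's only published benchmarks for what the trial could have found on pain. If they do not apply to the analysis reported, readers may take a null result as excluding effects that the trial had a lower chance of detecting.

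**Working it through.** **Inputs from the plan (Aim 2):** 20 surgeons per arm, 100 patients each, ICC 0.02, SD 20.8 (knee) and 20.9 (hip), alpha 5%. Sidedness is not stated; two-sided is assumed, since a one-sided test gives 2.82 points and does not match. Section 13 mentions no dropout and none is applied.

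**1. Reproducing the plan's figures.**

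- Design effect = 1 + (100 − 1) × 0.02 = 2.98. Effective n per arm = 2000 / 2.98 = 671.
- Standard error, knee = 20.8 × √(2/671) = 1.1355. With 38 df, detectable difference = (2.024 + 0.851) × 1.1355 = 3.26 points (hip 3.28), against the stated 3.3.
- Responders: power = Φ{(|p2 − p1| − 1.96√[2p̄(1 − p̄)/n]) / √[(p1(1 − p1) + p2(1 − p2))/n]}. For 77.9% vs 84.0% this is Φ{(0.061 − 0.0420)/0.0214} = 81.3%. For 90% vs 94.2% it is 81.5%.

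The arithmetic is sound, but the knee figure uses all 671 effective patients per arm and so does the hip figure. Neither leaves room for the other joint or for non-operative patients.

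**2. The figures as subgroup claims.** Assume that half of each surgeon's patients are knee-replacement patients. At 100 per surgeon, that is m = 50: design effect 1.98, effective n = 1000/1.98 = 505 per arm, detectable difference 3.76 points, power at 3.3 points 69%. At the current 3,000 (75 per surgeon, m = 37.5) the results are 4.06 points and 62%.

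**3. The responder outcome for all patients.** The documents give no operated share and no non-operative results. Assumptions: 30–70% operated with the knee rate of 77.9%; non-operative mean relief 5–15 points with SD 15–20.8; a non-operative responder is a normal value above 17.

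- Low end: 0.3 × 0.779 + 0.7 × P(Z > 12/15) = 0.38.
- High end: 0.7 × 0.779 + 0.3 × P(Z > 2/20.8) = 0.68.

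With ICC 0.02 throughout (effective n = 671 per arm at 4,000; 1500/2.48 = 605 at 3,000):

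| Control rate | Detectable, 4,000 | Power for 6.1 | Detectable, 3,000 | Power for 6.1 |
|---|---|---|---|---|
| 38% | 7.5 points | 62% | 7.9 points | 58% |
| 50% | 7.6 points | 61% | 8.0 points | 57% |
| 68% | 6.9 points | 69% | 7.3 points | 65% |

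**4. Mean pain relief for all patients.** Let q be the operated share, s_N the non-operative SD, gap the difference in mean relief, and s the between-surgeon SD of the operation rate.

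- W = q × 20.8² + (1 − q) × s_N²
- Total variance = W + q(1 − q) × gap²
- Between-surgeon variance = 0.02 × W + (s × gap)²
- ICC = between-surgeon variance / total variance

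All four quantities are assumptions. Selected results at 40 × 100:

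| q | gap | s_N | s | SD | ICC | Detectable | Power at 3.3 |
|---|---|---|---|---|---|---|---|
| 0.3 | 15 | 15 | 0 | 18.3 | 0.017 | 2.7 | 92% |
| 0.5 | 20 | 15 | 0.05 | 20.7 | 0.018 | 3.1 | 84% |
| 0.5 | 20 | 15 | 0.10 | 20.7 | 0.025 | 3.5 | 75% |
| 0.5 | 20 | 20.8 | 0.10 | 23.1 | 0.024 | 3.8 | 67% |
| 0.5 | 25 | 20.8 | 0.15 | 24.3 | 0.039 | 4.8 | 48% |

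The first and last rows are the extremes over q 0.3–0.7, gap 15–25, s_N 15 or 20.8 and s 0–0.15.

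**5. Decision quality.** This effect is standardised, so the population enters only through the ICC. At 40 × 100 (normal approximation) it is 0.153 SD at ICC 0.02, 0.177 at 0.03 and 0.216 at 0.05.

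**The case against.** The fairest defence is that section 13 attaches its pain and responder effects to knee- and hip-replacement patients by name, and never states 3.3 points or 6.1% for everyone. That is so, but the labels do not rescue the figures: as subgroup claims they spend the whole enrolment twice (step 1).

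Second, section 4 says that early study data were used to confirm 3,000 per aim. Those data may describe the right population. No revised mean, SD, rate or ICC is reported, however, and section 13 keeps the old inputs. This shows that the fix is feasible, not that it has been made.

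Third, the planned mixed models may adjust for baseline pain and function. If covariates explained 20–30% of the variance (an assumption), the 67% row in step 4 would rise to about 76–82%. The plan quantifies no such gain and bases its power on t-tests.

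Fourth, the plan is dated December 2021 and enrolment ends about March 2022, so restating power changes no enrolment or analysis. That stands, and it limits the consequence to interpretation.

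A reader might also infer more than the documents allow:

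- **That mixing must widen the SD, so that the trial is underpowered for mean pain relief.** This follows only if non-operated patients have an SD near 20.8. The documents give none, and a smaller value can leave power above 80%.
- **That all the planning inputs are registry figures.** Only the ICC is attributed to FORCE-TJR. The rest are labelled as knee- and hip-replacement figures, and their source is not stated.
- **That the decision-quality figure falls too.** It depends on the population only through its ICC.

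**Conclusion.** The point holds for pain relief and responders. The stated power of at least 80% is not supported on either reading: as all-patient figures the inputs describe operated patients only, and as knee or hip figures each assumes that every enrolled patient is of that type.

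The responder claim is the firmer part. Across assumed control rates of 38–68%, power for 6.1 percentage points is 61–69% at 4,000 patients and 57–65% at 3,000, with the plan's own ICC. For mean pain relief the documents settle neither size nor direction: power at 3.3 points runs from about 48% to 92% at 4,000 patients, depending on four quantities they do not give. The knee example (3.8 points, 69%) rests on an assumed half share. It follows that the benchmarks are unsupported for the planned analyses, not that the trial is shown to be too small.

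**What to change.** Restate the section 13 estimates at 3,000 patients per aim:

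1. For the all-patient analysis, report the operated share, SD, ICC and responder proportion from the early Aim 2 data, pooled across arms, and give the detectable pain and responder differences that follow.
2. Recompute the knee and hip figures with the expected number of each per surgeon.
3. Do not state at least 80% power at 3.3 points, or at 6.1% and 4.2%, unless those inputs support it.
4. Check the ICC behind the 0.16 SD decision-quality figure; the population question requires nothing more there.

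The cost is a short recalculation from early study data that section 4 says were already used, and stated figures that may be less favourable. No extra patients are needed.
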